6.1 Guiding principles and analysis strategy

Data will be analyzed on intent-to-treat basis. To allow for an analysis “as randomized” in the presence of missing data, we will impute missing data of the primary outcomes of the longitudinal study using a multiple imputation strategy under the *missing at random* assumption (see section 6.3 below). Data management, data cleaning, and statistical analyses will be done using Stata 17.0 (Statacorp, USA). The statistical significance will be set at 5%. All statistical tests will be two-sided. The analysis of primary study outcomes will not be adjusted for multiple testing (n=3 primary study outcomes) given the data involved represent three distinct experimental and control study samples with each one primary study outcome.

We will present results from non-adjusted and adjusted linear mixed effects regression models.

The non-adjusted models to analyze cohort 1 and 3 data will use *village (cluster)* as a random intercept and sampling stratum as a fixed effect to represent the study design. The non-adjusted models to analyze cohort 2 data will include sampling stratum as a fixed effect and will use a random intercept at the health center level and a random slope at the village level, to account for nesting of villages (clusters) into health centers (where treatment occurs for children from several villages).

In addition, we will conduct adjusted analyses, adjusting for the following variables:

- covariates that appear imbalanced at enrollment (absolute difference >10 pp) and are unlikely to have been impacted by exposure to the intervention before 6 months of age (cohort 1 and 3; virtually no household, parental or sociodemographic child level data collected at admission in cohort 2).
- child sex, and whether child was the first live birth, since a recent meta-analysis has reported that imbalance in child nutritional status between study groups can be associated to the imbalance in child sex and primiparity (3) (all adjusted models, except that data on first live birth are missing for cohort 2).
- month of enrollment (longitudinal models, cohorts 1 and 3) or month of admission into treatment (cohort 2).
- Child age at enrollment (cohort 3; constant in cohort 1; not detailed in MAM treatment registers used for cohort 2).
- type of nutrition unit where the child is/was treated (cohorts 2 and 3).

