3.5 Sample Size

3.5.1 Cohort 1 – primary outcome: longitudinal prevalence of wasting

The main cohort (#1) will include 1,750 children in the community aged 6 to 6.9 months, included for a period of 7 months and followed up monthly until the end of the study (total duration: 9 months).

The main cohort (#1) will include children aged 6-6.9 months. Given the small size of most villages and the sample size needed to detect a significant, plausible and meaningful difference in longitudinal wasting prevalence (primary outcome) between groups, we have calculated that we need to include an average of 3 children per month for 7 months in the 50 largest villages (25 villages in the control group and 25 in the intervention group) and an average of 2 children per month for 7 months in the 50 smallest villages in the study area (i.e., the medium-sized villages in the Mongo Health District: equally 25 in the control group and 25 in the intervention group). The children will all leave the cohort in the same month: counting the month of inclusion, the children will be seen for a maximum of 9 months (for children included at the start of the study) and a minimum of 3 months (for children included during the 7th month). This will result in a total sample of 1,750 children (10,500 visits in total of which 1,750 inclusions and 8,750 follow-ups). With 15% dropout, **the size of this study would provide sufficient power to detect a relative decrease of about 35% in the longitudinal prevalence of wasting**, with a power of 80% and a statistical significance of 5%, taking into account the cluster effect at the village level and the imbalance in cluster size.

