6.3 Treatment of missing data for primary study outcomes

For cohort 1 and 3, we will conduct multiple imputation of missing longitudinal anthropometric data using chained regressions (Stata: `mi impute chained (regress)`) which imputes missing values under the missing at random assumption⁶. Imputation variables will be the wide-form anthropometric measurements and child age, and complete predictors (independent variables) will be child sex and randomization stratum. We will use 50 imputations (Stata: `add`) with 10 iterations within imputation (Stata: `burnin`) to allow for convergence to a stationary distribution before the imputation. We will inspect imputation quality using trace plots by iteration to assess convergence and box plots to compare distributions of observed and imputed values. In addition, we will examine the fit of imputed child length values along the growth curves.

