6.4 Impact assessments

6.4.1 Main analyses

Impact on wasting longitudinal prevalence (primary outcome of cohort 1), wasting incidence (primary outcome of cohort 3), MAM and SAM longitudinal prevalence and incidence, and morbidity longitudinal prevalence, will be estimated using a mixed effects Poisson regression model with robust estimation of standard errors.

For other longitudinal outcomes, we will use linear mixed-effects regression models to assess the impact of the intervention on continuous outcomes and linear probability mixed-effects regression models with robust estimation of standard errors to assess the impact of the intervention on binary outcomes (19). Repeated visits within a child in longitudinal models will be accounted for by including a random intercept at the child level and a random slope at the visit level (defined as number of months since enrollment). For longitudinal models with continuous anthropometric outcomes (growth curves analyses), we will assess if the addition of a quadratic term of time (visit) improves the model fit significantly by applying a likelihood ratio test comparing the model with and without the quadratic term. To assess the specific

⁶ De Silva AP, Moreno-Betancur M, De Livera AM, Lee KJ, Simpson JA. (2017) A comparison of multiple imputation methods for handling missing values in longitudinal data in the presence of a time-varying covariate with a non-linear association with time: A simulation study. *BMC Med Res Methodol*; 17:1–11

impact of the intervention from enrollment at the age of 6 months to the end of follow-up, we will assess the interaction between intervention allocation and time (visit).

For cross-sectional analyses on outcomes measured at exit from cohorts 1 and 3 (mainly cumulative outcomes such as knowledge, vaccination, stunting, etc...) and on cohort 2 outcomes, we will use linear probability mixed-effects regression models with robust estimation of standard errors to assess the impact of the intervention on binary outcomes (including recovery rate, primary outcome of cohort 2), and linear mixed-effects regression models to assess impacts on continuous outcomes (19).

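### As written, end-of-study HAZ and stunting use only children with an exit visit, although the plan already imputes length and age (minor, secondary outcomes only)

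*SAP*

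**What the plan says.** SAP 6.1 sets intent-to-treat as the principle for all analyses. To honour it when data are missing, "we will impute missing data of the primary outcomes of the longitudinal study using a multiple imputation strategy", under missing at random. The heading of SAP 6.3 keeps the same scope: "Treatment of missing data for primary study outcomes".

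The body of 6.3 describes more than a wasting indicator. For cohorts 1 and 3, "we will conduct multiple imputation of missing longitudinal anthropometric data using chained regressions". "Imputation variables will be the wide-form anthropometric measurements and child age", and "complete predictors (independent variables) will be child sex and randomization stratum". Length is among the imputed measures, since the plan adds: "In addition, we will examine the fit of imputed child length values along the growth curves".

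SAP 3.4.2 lists mean HAZ, stunting, mean hemoglobin and anemia at the end of the study as secondary outcomes of cohorts 1 and 3. SAP 6.4.1 gives the models "For cross-sectional analyses on outcomes measured at exit from cohorts 1 and 3" and names stunting, knowledge and vaccination as examples. SAP 6.2.2 says that exit analyses do not adjust for the enrollment value of the outcome. None of these sections says what happens to a child with no exit visit.

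The only attrition figure is in the cohort 1 sample size (SAP 3.5.1): "With 15% dropout". SAP 3.5.3 gives none for cohort 3.

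**The concern.** A cross-sectional model has one record per child. If that record is missing and imputation is reserved for the primary outcomes, the child leaves the analysis. Earlier measurements of the same child then enter the exit contrast neither by imputation nor as a covariate.

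Exit HAZ and stunting will be reported beside a primary analysis that keeps every randomized child, so readers may assume the same population. Two things are at stake. One is precision, because a child's last recorded length predicts exit length closely. The other is bias, if the link between poor growth and leaving the study differs between arms. Such a difference is possible in an unblinded trial in which only intervention households receive program visits and monthly inputs, but the documents give no evidence that it occurs.

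**Working it through.** **1. The plan's own counts (SAP 3.5.1).**
- Children: 50 × 3 × 7 + 50 × 2 × 7 = 1,750.
- Visits: 250 × (9+8+7+6+5+4+3) = 10,500, of which 10,500 − 1,750 = 8,750 are follow-ups.

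Both reproduce exactly. The detectable 35% decrease cannot be reproduced, because no baseline longitudinal prevalence or ICC is given for cohort 1. This point does not depend on it.

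**2. Children without an exit value (cohort 1).** 0.15 × 1,750 = 262.5, so about 263 are lost and about 1,487 remain, or about 744 per arm.

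**3. What is already imputed.** Exit HAZ needs length, age and sex. SAP 6.3 imputes length and age at each visit and has sex as a complete predictor. Study arm and village are not among the listed predictors.

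**4. Precision under random dropout.** The variance of the difference is proportional to DE/n per arm, with DE = 1 + (m − 1) × ICC. The mean cluster size m is 17.5 with everyone and 17.5 × 0.85 = 14.875 for completers.
- HAZ, assumed ICC 0.03: DE is 1.495 on 875 per arm, against 1.416 on 743.75. The SE ratio is √[(1.416/743.75)/(1.495/875)] = 1.056.
- Stunting, assumed prevalence 30% and ICC 0.02: SE = √(2 × 0.3 × 0.7 × DE/n), which is 2.5 points with 1,750 children and 2.7 with 1,487.

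In simulation, the HAZ standard error is about 3% to 6% larger for completers than with imputation.

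**5. Bias in exit HAZ.** Simulated trials had 50 villages of 21 children and 50 of 14. Assumptions, none of them in the documents: true HAZ difference 0.10, ICC 0.03, residual SD 0.4 for exit HAZ given the last HAZ, about 15% lost. The log-odds of loss change by b per z of HAZ.

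| Selection b (control / intervention) | Completers only | Imputed, arm included |
|---|---|---|
| 0 / 0 (random) | no bias | about 0.10 |
| −0.5 / −0.5 | about 0.095 | about 0.10 |
| −0.5 / −0.3 | about 0.064 | about 0.10 |
| −0.5 / 0 | about 0.02 | about 0.10 |

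The third row loses (0.10 − 0.064)/0.10 = 36% of the effect, about one third. In the last row the overall losses are 16% and 15%, so a table of attrition rates would show little. The imputed column recovers the truth because loss depends on observed HAZ, so missing at random holds by construction, and because arm is in the imputation model.

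**6. Hand check for stunting.** Assume 30% stunting in both arms, so the true difference is zero. Prevalence among completers is (0.30 − d × s)/(1 − d), where d is the loss and s the stunting prevalence among lost children.
- d = 15% and the same s in both arms: difference 0.
- d = 20% in control and 10% in intervention, s = 40%: (0.30 − 0.08)/0.80 = 27.5% against (0.30 − 0.04)/0.90 = 28.9%, a spurious 1.4 points.
- d = 15% in both arms, s = 40% in control and 30% in intervention: (0.30 − 0.06)/0.85 = 28.2% against 30.0%, a spurious 1.8 points.

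The SE is about 2.7 points, so these biases are below one standard error.

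**The case against.** The strongest reply is that the plan already uses lost children's lengths. Linear growth rate is a separate secondary outcome, and the growth-curve models of SAP 6.4.1 take in all observed visits, with child-level random effects and an arm-by-time term. They are valid under the same missing-at-random assumption that imputation needs. This stands. A reader might infer that lengths recorded before dropout are thrown away throughout. They are not; the gap concerns the exit contrasts only.

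Second, the SAP never calls these analyses complete-case, and the body of 6.3, which imputes anthropometry across visits, could be read as covering the exit visit. That is fair, but both statements of scope confine imputation to primary outcomes, so the literal reading excludes children without an exit visit. One sentence would settle it.

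Third, a reader might infer that exit HAZ and stunting will be badly distorted. The documents do not support that. Most of the effect disappears only in the simulated case where selection occurs in one arm alone. Survey teams visit both arms monthly, and similar selection in both arms is nearly harmless.

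Fourth, it is tempting to say that every exit outcome is measured once, or that the imputed lengths can be reused as they are. Length is measured monthly and hemoglobin also at enrollment. The listed imputation predictors omit arm, so reuse without adding it would pull the exit contrast toward no difference.

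**Conclusion.** The point holds as a limited gap. As written, end-of-study mean HAZ and stunting rest on children with an exit visit, although most of the machinery to include the others is already specified. For cohort 1 that means about 1,487 of 1,750 at the planning dropout. The 15% should not be carried over to cohort 3, which has no stated figure.

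The certain cost is small: 3-6% in the standard error for HAZ. The size and direction of any bias are unknown. Under the stated assumptions it runs from near zero (similar selection in both arms) through about one third of the effect (−0.5 against −0.3 per z) to most of it (one arm only). Severity is minor: only secondary outcomes are affected, and the longitudinal growth models give a partial safeguard.

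**What to change.** In SAP 6.3, state that exit HAZ and stunting for cohorts 1 and 3 are derived from the imputed length and age at each child's scheduled exit visit. That visit should follow the revised exit rules in SAP Table 2: exits split over the last two months in cohort 1, and six months or study end in cohort 3. Add study arm, and preferably village, to the imputation predictors. Impute no values after death. Report complete-case results as a sensitivity analysis.

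Optionally, add exit hemoglobin to the chained model, with enrollment hemoglobin and anthropometry as predictors.

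The cost is a few lines of SAP text and a little more code. The exit results would then rely on missing at random, which the plan already accepts for its primary outcomes.

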3.2 Study design

We designed a two-arm, cluster-randomized, non-blinded, longitudinal, effectiveness trial to study the impact of the PASIM intervention as compared to the standard of care in the study area. Two study groups will be formed, a control/comparison group, and an intervention group receiving the integrated package of interventions. The activities of the control and intervention group are summarized in Table 1.

Table 1: intervention package in intervention and comparison groups

	Intervention	Comparison
Prevention	Integrated community care group (CCG) Weekly home visits: BCC (pregnancy to 23 mo) Monthly village-level distribution in presence of CCG volunteer of 360 g of soap + 1 L of bleach + 3 kg of CSB++ (non wasted 6-11 mo) MNPs (12-23 mo)	No intervention (some pre-existing CCG with no support since 2019; some areas with punctual preventive interventions)
Screening	Family MUAC (6-23 mo) Integrated CCG (6-23 mo) Weekly home visits: training and supervision of family MUAC, MUAC screening, referral, follow-up on referral through supervisor (NGO promoter)	No intervention (Contact with existing CCG and health system ; some areas with caregivers trained to family MUAC in 2019)
Treatment	Current CMAM protocol (adapted), health center or community site (6-59 mo) SAM/MAM treatment, MUAC only, reduced intensity, culinary demonstrations at community sites Strengthened RUTF/RUSF supply chain Integrated CCG (6-23 mo) Weekly home visits: general and AM specific counselling, ensure RUSF/RUTF compliance Monthly village-level distribution in presence of CCG volunteer of 360 g of soap + 1 L of bleach (6-23 mo)	Same as for intervention group Strengthened RUTF/RUSF supply chain No intervention
Relapse prevention	Integrated CCG Weekly home visits: specific counselling on IYCF (6-23 mo for 6 mo) Monthly village-level distribution in presence of CCG volunteer of 200 g of soap + 400 mL of bleach + 3 kg of CSB++ (6-23 mo for 6 mo)	No intervention

Abbreviation used: BCC, Behavior Change Communication; CCG, Integrated community care group; CMAM, Community-based management of acute malnutrition; CSB++, improved corn-soy-blend for young children; MAM, Moderate wasting; MNPs, Micronutrients powder; MUAC, Mid-upper arm circumference; RUSF, Ready-to-use supplementary food; RUTF, Ready-to-use therapeutic food; SAM, Severe wasting.

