3.6 Sampling and study inclusion criteria

Details on the selection of children, inclusion and exclusion criteria, and changes to the protocol, are given in Table 2.

Table 2: Selection of study participants, inclusion and exclusion criteria, sample size and follow-up details for the 3 study cohorts.

	Main cohort	Treatment cohort	Relapse prevention cohort
Selection of participants	In each village, random selection from a randomly ordered census list of children aged 0-6 months (census conducted by the survey team in the first month of the survey), prepared by an investigator based in Dakar using Stata software. Children not meeting inclusion criteria (see below) will be replaced until the maximum number of children is met (3 times the number of months of inclusion), or until the list of eligible children is exhausted.	All records of children (aged [6-23] months) living in the 100 most populated villages in the study area and admitted during the study in a treatment program by the national CMAM program. Treatment data will be collected by the CMAM treatment units as part of their routine. Each treatment unit will be visited by an enumerator who will be responsible for monitoring data quality and copying anonymous data from the registers to electronic forms.	All available children in each village who will be discharged from CMAM treatment (based on treatment unit registers) and recovered will be invited to participate in the study until the required sample size is reached for each village (8 children). In villages with more children than necessary, the study team will invite children to participate in the order of a randomly ordered list prepared by an investigator based in Dakar using Stata software.
Inclusion criteria	6-6.9 months of age. Child singleton. Resident of the village. Consent of the mother or guardian.	Child admitted for treatment in a national treatment program. 6-23 months of age at admission. Child lives in one of the 100 villages in the study area.	Child has been successfully treated for wasting (defined as MUAC ≥ 125 mm) and has been discharged from the national treatment program within the last 30 days. 6-23 months of age at inclusion. Child singleton.

	Main cohort	Treatment cohort	Relapse prevention cohort
			Resident of the village. Consent of the mother or guardian.

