6.2 Enrollment characteristics

6.2.1 Characteristics of study groups at enrollment

The presentation of enrollment characteristics (see Table 3) will be done as follows:

- Categorical variables: frequencies and percentages, as appropriate. Percentages will be calculated based on the number of participants for whom data are available.
- Continuous variables: mean and SD or median and interquartile range, as appropriate.

Following the CONSORT guidelines, we will not statistically test for differences between study groups at enrollment in cohort 1 (18). Imbalance will be considered for absolute differences >10 pp (binary

outcomes) or >10 % (continuous outcomes). However, as the intervention risks impacting the size and characteristics of the study population for cohort 3 (if it impacts who is wasted, and then treated and cured from wasting), we will test baseline differences across groups in cohort 3, using linear (continuous outcomes) and linear probability (binary outcomes) mixed-effects regression models with robust estimation of standard errors, considering the cluster as a random effect, and strata and intervention as a fixed effect.

Table 3: Enrollment characteristics for cohorts 1 and 3

Characteristics	Comments/References
Household level	
HH size (mean/SD)	
Number of under 5 children in household (mean/SD)	
Number of adults (15-64 y) (mean/SD)	
Polygamous HH(%)	
HH food insecurity (mean and proportion of food secure HH)	Coates J, Swindale A, Bilinsky P. Household Food Insecurity Access Scale (HFIAS) for measurement of food access: indicator guide. Washington, DC: FANTA; 2007. https://doi.org/10.1007/s13398-014-0173-7.2
SES status classification (tertiles, %)	Principal component analysis will be used to construct a proxy household Socio-Economic Score (SES) using ownership of various assets (an asset is excluded if ownership is below 5% or above 95% on HH level), housing materials, primary source of lighting, primary energy source, and home ownership. Tertiles of the first principal component (i.e., the one with the highest eigenvalue) will be used.
Improved water treatment technologies used (%)	USAID (2021) Water and development- Indicator handbook. Washington DC
Improved sanitation facility (%)	USAID (2021) Water and development- Indicator handbook. Washington DC
Handwashing station with soap available (%)	USAID (2021) Water and development- Indicator handbook. Washington DC

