6.2.2 Specific considerations on the use of enrollment data

Children will be enrolled in the cohort 1 at the age of 6 months, when the program foresees MUAC screening measurements and inputs distribution to start. However, community care groups in the intervention study arms are tasked to conduct home visits to pregnant and lactating women and caregivers of children up to 24 months of age to provide BCC on child nutrition, health and WASH.

Therefore, it is likely that caregivers with children of 6 months enrolled in the cohort after the start of the program have been exposed to BCC prior to study inclusion in the intervention group. Similarly, it is likely that children enrolled in cohort 3 after the start of the program have been exposed to BCC, MUAC screening or inputs distribution prior to study inclusion in the intervention group. For this reason, all longitudinal analyses of cohort 1 and cohort 3 data will include the data at enrollment as impact data, and analyses studying impacts at exit will not control for enrollment value of the outcome. For study outcomes related to activities that only start between the age of 6 and 7 months, like MUAC-based screening and the distribution of inputs, we will consider data related to the program's impact from the child age of 7 months onwards.

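### The covariate filter in SAP 6.1 checks only exposure before 6 months of age, so in cohort 3 it can admit variables the package has already shifted into the adjusted relapse model

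*SAP*

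**What the plan says.** SAP 6.1 reports a non-adjusted and an adjusted model for each outcome. The adjusted model takes in "covariates that appear imbalanced at enrollment (absolute difference >10 pp"), provided that they "are unlikely to have been impacted by exposure to the intervention before 6 months of age (cohort 1 and 3"). One filter, with one age limit, serves both cohorts. SAP 6.2.1 adds that continuous variables count as imbalanced when they differ by more than 10%.

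The cohorts enter at different points. SAP 6.2.2 puts cohort 1 entry at the age when screening and inputs begin (the quote stops one word short of the sentence's end): "Children will be enrolled in the cohort 1 at the age of 6 months, when the program foresees MUAC screening measurements and inputs distribution to". Cohort 3 entry in SAP Table 2 is "6-23 months of age at inclusion. Child singleton", after discharge from treatment. SAP 6.2.2 then says that "it is likely that children enrolled in cohort 3 after the start of the program have been exposed to BCC, MUAC screening or inputs distribution" before they joined.

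SAP Table 1 dates the inputs. The preventive supplement is "3 kg of CSB++ (non wasted 6-11 mo"). During treatment the intervention group has "Monthly village-level distribution in presence of CCG volunteer of 360 g of soap + 1 L of bleach (6-23 mo"), with no counterpart from care groups in the comparison group. Behavior change communication runs from pregnancy.

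The candidate covariates for both cohorts are in SAP Table 3. They include water treatment, a handwashing station with soap, several child diet indicators, hemoglobin, anthropometry and caregiver knowledge.

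**The concern.** The filter's evident purpose is to keep variables that the intervention has changed out of the adjusted models. In cohort 1 the age limit does this, because exposure before 6 months and exposure before enrollment are nearly the same thing. In cohort 3 they are not: a child can spend more than a year in the program between 6 months and enrollment, and none of that exposure is screened.

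The clearest route is soap and bleach. Intervention children in treatment receive both every month; at cohort 3 enrollment the survey then records handwashing soap and water treatment. A gap of more than 10 percentage points is what a working program would produce, and that same gap triggers adjustment. If better hygiene or diet is part of how the package prevents relapse, conditioning on it takes that part out of the estimate. Relapse incidence is the primary outcome of cohort 3, so a reader who sees the two estimates diverge could not tell whether adjustment removed confounding or removed effect.

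**Working it through.** The plan states no figure on this point, so there is none to reproduce. The check sets the texts side by side and then asks how far the window misses cohort 3.

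**Texts compared**

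| | Cohort 1 | Cohort 3 |
|---|---|---|
| Age at enrollment (SAP Table 2) | 6-6.9 months | 6-23 months, after treatment |
| Exposure before enrollment (SAP 6.2.2) | communication only | communication, screening or inputs |
| Window screened (SAP 6.1) | before 6 months | before 6 months |
| Exposure left unscreened | under 1 month | everything from 6 months to enrollment |

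No other sentence closes the gap. SAP 6.2.2 bars adjustment for the outcome's own enrollment value, and only in analyses at exit. SAP 3.2 and 6.2.1 call for caution and for testing cohort 3 baseline differences, but leave the covariate rule as it is.

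**How many cohort 3 children the window cannot describe**

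Assumptions: the program started with the study in April 2021, and age at inclusion is uniform. From the documents: cohort 3 inclusion starts in the second study month (Protocol Table 1), was planned for 2 months, and was extended to 7 and then 9 (SAP Table 2).

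A child included *t* months after program start was already at least 6 months old at that start if age is at least 6 + *t*. With ages uniform on 6-24 months the share is (18 - *t*)/18:

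- 2-month inclusion, *t* from 1 to 3, mean 2: 16/18 = 89%
- 7-month inclusion, *t* from 1 to 8, mean 4.5: 13.5/18 = 75%
- 9-month inclusion, *t* from 1 to 10, mean 5.5: 12.5/18 = 69%

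With younger ages, uniform on 6-15 months, the share is (9 - *t*)/9, and zero beyond *t* = 9:

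- 2 months: 7/9 = 78%
- 7 months: 4.5/9 = 50%
- 9 months: the integral of (9 - *t*)/9 from 1 to 9 is 64/18 = 3.56; divided by 9 months, 40%

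**What adjustment could do to the estimate (illustration only)**

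Take the 33% reduction used for cohort 3 in SAP 3.5.3 as the true effect (rate ratio 0.67), and suppose that a share *s* of the log rate ratio runs through adjusted variables. The documents give no value for *s*. The adjusted ratio is 0.67^(1 - *s*). Power, from an assumed 80% at two-sided 5% with the standard error held fixed, is Φ((1 - *s*) × (1.960 + 0.842) - 1.960).

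| *s* | Rate ratio | Power |
|---|---|---|
| 0 | 0.67 | 80% |
| 10% | 0.70 | 71% |
| 25% | 0.74 | 56% |
| 50% | 0.82 | 29% |

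This covers mediation only. It does not describe imbalance that comes from selection.

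**The case against.** Five replies deserve weight.

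- *The filter screens variables, not children.* A reader might infer from the shares above that it excludes nothing in cohort 3. That does not follow. Behavior change communication on nutrition, health and hygiene begins in pregnancy, so an analyst could judge caregiver knowledge, and perhaps some practices, to be open to influence before 6 months and bar them in both cohorts. This stands, and the shares do not count how many mediators would enter. But a change caused by inputs that begin at 6 months or later is outside the wording, and a pre-specified rule should not need a generous reading to do its job.
- *Enrollment anthropometry is an unlikely entrant.* Mean MUAC must differ by more than 10%; with entry at 125 mm or more that is at least about 12.5 mm. SAP 6.2.2 also treats enrollment data as impact data in the longitudinal analyses, so adjusting for WLZ would sit badly with it, although it is not expressly barred in the incidence model. This stands; binary hygiene and diet items are the realistic route.
- *The non-adjusted estimate is untouched.* This stands. It contains only village and stratum. The SAP presents the adjusted models as an addition and never calls them primary, so the text does not support reading the primary relapse result as a whole as biased.
- *Adjustment may help.* SAP 3.2 calls cohort 3 quasi-experimental, and SAP 6.2.1 says that "as the intervention risks impacting the size and characteristics of the study population for cohort 3". Some imbalance may be selection, where adjustment can reduce bias. This stands, and it leaves the net direction open.
- *The rule permits mediators; it does not require them.* True. Yet variables the package targets are among those most likely to cross the imbalance threshold.

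**Conclusion.** The concern holds for the adjusted cohort 3 relapse model. A window that suits cohort 1 is applied unchanged to a cohort that the SAP itself says is exposed later, and the rule as written can admit input-driven hygiene and feeding variables as adjusters.

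How much this would change the estimate cannot be worked out from the documents. The 89% to 40% range for children beyond the window's reach depends on an assumed program start and age distribution; it is not safe to state as fact that most cohort 3 children had passed 6 months when the program began. The 0.70 to 0.82 range depends on assumed mediated shares. The finding rests on the text and needs neither range. It warrants correction before analysis, and it does not undermine the trial's conclusions by itself.

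**What to change.** In SAP 6.1, keep the present window for cohort 1. For cohort 3, replace it with: *unlikely to have been impacted by any exposure to the intervention before cohort 3 enrollment*. Eligible adjusters are then characteristics that the package does not target, such as parental schooling, household structure and distance to the health center. State that water, hygiene and feeding practices are not eligible in cohort 3.

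Do not ban enrollment anthropometry, hemoglobin and food security outright, since they may carry information on selection. Label any cohort 3 model that adds them as a sensitivity analysis, and say that it may remove part of the effect along with the selection bias.

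The cost is a few sentences and no new data. The downside is fewer candidate adjusters for selection in cohort 3.
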